## **8.2 ORDERING INVESTIGATIONAL AGENTS**

---

Once the clinical trial site receives regulatory approval (IRB/IEB), and the Sponsor and/or Sponsor designee performs the Site Initiation Visit and inspection of pharmacy, and determines the site to be officially open for enrollment, an automatic shipment of pre-determined quantity of both drugs will be shipped to the clinical trial site.

Upon receipt of treatment supplies, the Pharmacist or the appropriate person of the site should update the accountability forms.

If any abnormality on the supplied boxes is observed, the Pharmacist or the appropriate person must document that on the acknowledgement of receipt and contact that Sponsor and/or Sponsor designee.

## 9 STATISTICAL CONSIDERATIONS

---

This section describes the statistical methods to be used to analyze the efficacy and safety endpoints. A formal statistical analysis plan (SAP), which must be finalized before database lock, will provide additional details for data handling procedures, statistical methods, and data presentations (e.g., table, listing, and figure shells). The final clinical study report will describe deviations from the SAP, if any.

### 9.1 SAMPLE SIZE AND POWER

---

### 9.2 GENERAL ANALYSIS CONVENTION

---

Unless otherwise stated, all analyses will be performed using SAS Version 9.2 or higher and all hypothesis tests will be conducted at a two-sided significance level of 0.05. P-values will be presented with 3 decimals and p-values that are less than 0.001 will be presented as <0.001.

Continuous (non-survival related) data will be summarized using descriptive statistics: number of observations (n), mean, standard deviation (SD), median, 25th and 75th percentiles, minimum, and maximum. Frequencies and percentages will be used to summarize categorical (discrete) data. Presentations of categorical data will generally suppress percentages for items where the count is zero in order to draw attention to the nonzero counts. In general, mean, standard deviation, median, 25th and 75th percentiles, minimum, maximum, and percentages will be presented with one decimal.

### 9.3 ANALYSIS POPULATIONS

---

The Intent-to-Treat (ITT) population will consist of all subjects who receive at least one dose of study drug and provide some efficacy values. The primary efficacy analyses will be performed based on the ITT population.

The Safety Population will include all subjects who receive at least one dose of study drug. All safety assessments including toxicity will be performed on the Safety Population.

The modified intent-to-treat Population (mITT) will consist of all subjects who have received UTX and have one baseline and post-baseline MRI without a major protocol deviation. The criteria for a major protocol deviation will be determined and documented prior to data base lock. Subject exclusion from the mITT population will also be determined and documented prior to database lock. Supportive analyses may be performed based on the mITT population.

### 9.4 SUBJECT DISPOSITION

---

The disposition of subjects includes the number and percentage of subjects for the following categories: subjects enrolled, subjects treated (safety population), subjects in the ITT population, Subjects in the mITT population, if applicable, subjects completed, and subjects discontinued from the study. The reasons for study discontinuation will also be summarized in this table. Only one primary reason for study discontinuation will be reported in the summary. However, all reasons will be presented in the listing.

A listing will present data concerning subject disposition.

## 9.5 SUBJECT DEMOGRAPHICS AND BASELINE CHARACTERISTICS

---

Baseline demographic and clinical characteristics will be summarized as percentages for categorical variables and as mean, standard deviation, median, minimum and maximum for continuous measures. The analyses of baseline characteristics will be presented for the ITT Population.

## 9.6 MEDICAL HISTORY

---

Medical history will be captured at the Screening visit. Medical history will be coded using MedDRA and will be listed and may be summarized by MedDRA system organ class and preferred term for the Safety population, if deemed necessary.

## 9.7 EXTENT OF EXPOSURE

---

The dose (mg) of study drugs administered, the total number of doses of study drugs, and the duration of treatment will be summarized with descriptive statistics. The number and percentage of subjects whose dose is modified at any time will be summarized by infusions and overall. The proportion of subjects completing each infusion of treatment will be summarized.

## 9.8 EFFICACY ANALYSES

---

The study is not designed (powered) to detect treatment differences. All efficacy variables will be summarized at all-time scheduled points where they are assessed. If appropriate, dose response or treatment differences may be analyzed. If p-values are presented, they will be nominal p-values without adjustment for multiple tests.

### 9.8.1 PRIMARY EFFICACY VARIABLE

---

The primary efficacy variable will be responder rate at week 4 (2 weeks after the second infusion (day 15)), where responders are subjects who have reduced B-cell depletion by  $\geq 95\%$ . The percentages of the responders will be presented. The 95% confidence intervals of the percentages may be presented, if appropriate, using exact method due to small sample size. Logistic analysis may be used to perform trend tests to assess dose response.

### 9.8.2 SECONDARY EFFICACY VARIABLE

---

The secondary efficacy variables include:

- Number of new Gd-enhancing lesions at 24 and 48 weeks
- Number of new or enlarging T2 lesions at 24 and 48 weeks
- Annualized relapse rate (ARR)
- Relapse rate reduction (RRR)
- Percent of relapse free subjects
- Reduction in B cells (CD19+), memory (CD19+CD27+) and naïve (CD19+CD27-) B cells at baseline, day 1 (pre dose) and 2; week 2; Day15 (pre-dose); week 4 and every 4 weeks thereafter until the next infusion at week 24 (pre-dose and 2 days post-dose) 25, 28, 36, 40, 44 and 48
- To examine sustained B cell reduction during the first and third infusions
- Additional immune profiling (CD4+, CD8+, IL10 and NK cells) at baseline, day 1 (pre dose) and 2; week 2, Day 15 (pre-dose); week 4 and every 4 weeks thereafter until the next infusion at week 24 (pre-dose and 2 days post dose) 25, 28, 36, 40, 44 and 48
- PK (ADME) profile of ublituximab at day 1 (pre-dose); week 2; day 15 (pre-dose); weeks 4, 24 (pre-dose) and 25

All these variables will be summarized. Dose response and treatment difference may be analyzed as appropriate. Additional efficacy variables may be included as appropriate.

## 10 SAFETY REPORTING AND ANALYSIS

---

### 10.1 SAFETY ANALYSES

---

Safety evaluations will be based on the incidence, intensity, and type of adverse events, as well as on clinically significant changes in the patient's physical examination, vital signs, and clinical laboratory results. Safety analyses will be performed using the safety population. Safety variables will be tabulated and presented by the dose of ublituximab actually received. Exposure to study treatment and reasons for discontinuation of study treatment will also be tabulated. Must obtain expert evaluations of brain MRI images of subjects with suspected opportunistic CNS infections including PML.

### 10.2 ADVERSE EVENTS

---

Adverse event (AE) monitoring and reporting is a routine part of every clinical trial. The following list of AEs and the characteristics of an observed AE (Section 8.1.1) will determine whether the event requires expedited reporting in addition to routine reporting.

### 10.3 ADVERSE EVENT CHARACTERISTICS

---

**CTCAE term (AE description) and grade:** The descriptions and grading scales found in the revised NCI Common Terminology Criteria for Adverse Events (CTCAE) version 4.0 will be utilized for AE reporting. All appropriate treatment areas should have access to a copy of the CTCAE version 4.0. A copy of the CTCAE version 4.0 can be downloaded from the CTEP web site [http://ctep.cancer.gov/protocolDevelopment/electronic\\_applications/ctc.htm](http://ctep.cancer.gov/protocolDevelopment/electronic_applications/ctc.htm).

**'Expectedness':** AEs can be 'Unexpected' or 'Expected' for expedited reporting purposes only.

### 10.4 PROTOCOL-SPECIFIC EXPEDITED ADVERSE EVENT REPORTING EXCLUSIONS

---

**For this protocol only,** certain AEs/grades are exceptions to the Expedited Reporting Guidelines and do not require expedited reporting (i.e., MedWatch). The following AEs are considered expected and do not require expedited reporting.

CTCAE Category	Adverse Event	Grade	Hospitalization/ Prolongation of Hospitalization	Attribution
Blood/bone marrow	Neutropenia <7 days without fever	4	No	Yes
Blood/bone marrow	Thrombocytopenia <7 days without bleeding	4	No	Yes

### 10.5 ADVERSE EVENTS (AE'S) AND TREATMENT EMERGENT ADVERSE EVENTS (TEAE'S)

---

All AEs and SAEs occurring on study will be listed by patient. The frequency and percentages of subjects with treatment-emergent adverse events (TEAEs) will be tabulated by system organ class (SOC) and PT, where treatment-emergent is defined as any AE that:

- Occurs after first dosing of study medication and through the end of the study or up through 30 days after the last dose of study treatment, or

- Is considered treatment-related regardless of the start date of the event, or
- Is present before first dosing of study medication but worsens in intensity or the investigator subsequently considers treatment-related.

TEAEs that are considered at least possibly related to study treatment will be tabulated as well as deaths, SAEs, and events resulting in treatment discontinuation.

AEs that occur after informed consent but before first dosing of study medication will not be summarized but will be listed.

At each level of summarization, a patient will be counted only once for each AE, SOC, or PT experienced within that level. In the summation for AE severity, within each level of AE, SOC, or PT experienced, the one with the highest severity will be included. In the summation for AE's relationship to the study drug, within each level of AE, SOC, or PT experienced, the one with the closest relationship to the study drug will be included.

## 10.6 DEFINITIONS OF ADVERSE EVENTS

---

An adverse event (AE) is any untoward medical occurrence in a patient or clinical investigation patient administered a pharmaceutical product. An AE does not necessarily have to have a causal relationship with this treatment. An adverse event (AE) can therefore be any unfavorable and unintended sign (including an abnormal laboratory finding, for example), symptom, or disease temporarily associated with the use of a medicinal product, whether or not considered related to the medicinal product. This includes any occurrence that is new in onset or aggravated in severity or frequency from the baseline condition.

In clinical studies, an AE can include an undesirable medical condition occurring at any time, including run-in or washout periods, even if no trial treatment has been administered. The NCI Common Terminology Criteria for Adverse Events (CTCAE) v4.0 is to be used for the grading of severity of symptoms and abnormal findings. For adverse events not covered by the NCI-CTCAE Version 4.0 grading system, the following definitions will be used:

- **Grade 1:** Mild; asymptomatic or mild symptoms; clinical or diagnostic observations only; intervention not indicated.
- **Grade 2:** Moderate; minimal, local or non-invasive intervention indicated.
- **Grade 3:** Severe or medically significant but not immediately life-threatening; hospitalization or prolongation of hospitalization indicated.
- **Grade 4:** Life-threatening consequences; urgent intervention indicated.
- **Grade 5:** Death related to AE.

## 10.7 ADVERSE EVENTS / SERIOUS ADVERSE EVENT CAUSALITY ASSESSMENT

---

The Investigator must also assess the relationship of any adverse event to the use of study drug, (whether none, one, or all) based on available information, using the following guidelines:

1. **Not Related:** Clear-cut temporal and/or mechanistic relation to a cause other than the study drug.
2. **Doubtful:** There is no reasonable possibility that the event is related to the study drug but a definite cause cannot be ascertained.
3. **Possible:** There is still a reasonable possibility that the cause of the event was the study drug but there exists a more likely cause of the event such as complications of progressive disease.

4. **Probable:** The most likely cause of the event is the study drug but other causes cannot be completely excluded.
5. **Definite:** Clear cut temporal and/or mechanistic relation to the study drug. All other causes have been eliminated. Events classified as definite will often be confirmed by documenting resolution on discontinuation of the study drug and recurrence upon resumption.

In the summary of drug related AEs, Categories 1 and 2 will be considered as “Not Drug Related” and all other categories, including missing, will be considered as “Drug Related.”

---

### 10.7.1 RECORDING OF ADVERSE EVENTS

---

All adverse events of any patient during the course of the trial will be reported on the case report form, and the investigator will give his or her opinion as to the relationship of the adverse event to trial drug treatment (i.e., whether the event is related or unrelated to trial drug administration –ublituximab). If the adverse event is serious, it should be reported as soon as possible and no greater than 24 hours to the sponsor or designee. Other untoward events occurring in the framework of a clinical trial are also to be recorded as AEs (i.e., AEs that occur prior to assignment of trial treatment that are related to a protocol-mandated intervention, including invasive procedures such as biopsies, medication washout, or no treatment run-in).

All AEs regardless of seriousness or relationship to ublituximab treatment spanning from Day 1 until 30 calendar days after discontinuation or completion of either protocol-specific treatment as defined by the protocol for that patient, are to be recorded on the CRF.

---

### 10.7.2 ABNORMAL LABORATORY VALUES AND VITAL SIGNS

---

The reporting of abnormalities of vital signs as adverse events should be avoided. Abnormalities of vital signs should not be reported unless any criterion for an SAE is fulfilled, the vital signs abnormalities cause the patient to discontinue trial treatment, or the investigator insists that the abnormality should be reported as an AE. Abnormal laboratory results should be noted in the eCRF as an adverse event if they are associated with an overdose, require or prolong inpatient hospitalization, or are otherwise considered clinically significant by the investigator. If an abnormal laboratory value or vital sign is associated with clinical signs and/or symptoms, the sign or symptom should be reported as an AE, and the associated laboratory value or vital sign should be considered additional information that must be collected in the relevant eCRF. If the laboratory abnormality is a sign of a disease or syndrome, only the diagnosis needs to be recorded on the SAE Report Form or AE eCRF.

Clinical Laboratory Results will be summarized. Summary statistics for actual values and for changes from baseline will be tabulated for laboratory results by scheduled visit. Subjects with laboratory values outside of the normal reference range at any post-baseline assessment will be summarized, and graded per NCI CTCAE Version 4.0 when applicable. Patient incidence of laboratory toxicity will be summarized by treatment group and maximum grade for each laboratory test.

---

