## **5.2 AGENT ADMINISTRATION**

---

Treatment will be administered in the MS center. The MS centers must have skilled personnel and adequate equipment to provide emergency treatment should the subject experience anaphylaxis, hypotension or respiratory distress. Subjects will be enrolled into a specified cohort. A single dose of 150 mg of ublituximab on Day 1 with an infusion rate of 4 hours, 450 or 600 mg on Day 15 at different infusion rates (see dosing scheme), and at week 24, a single dose of 450 or 600 mg of ublituximab with different infusion rates will be administered to the respective cohorts. Additionally, 2 subjects in each cohort will be randomized to a placebo group. On day 28, the placebo subjects will begin active treatment with ublituximab in its respective cohort (see dosing scheme). Administration of ublituximab and placebo will be under the direction of the study investigators. Additional dosing cohorts may be explored.

It is required the absolute neutrophil counts and the platelet count should be within normal range before the infusion of ublituximab.

If the liver enzymes (ALT and/or AST) are > 5 times the upper limit of normal (ULN) of the normal range, or if the neutrophil count and platelets counts are below acceptable levels as described, the dose of ublituximab will be held for up to 48 hours until the laboratory values return to within acceptable range. If all labs above do not return to within the acceptable range within 48 hours, the subject will not receive the ublituximab infusion and will be withdrawn from the study. Subjects who are withdrawn will be asked to enter the follow-up evaluation period of the study.

---

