### 10.11.2 ABNORMAL LABORATORY VALUES

---

Abnormal laboratory results should be noted in the eCRF as an adverse event if they are associated with an overdose, require or prolong inpatient hospitalization, or are otherwise considered clinically significant by the investigator. If an abnormal laboratory value or vital sign is associated with clinical signs and/or symptoms, the sign or symptom should be reported as an AE, and the associated laboratory value or vital sign should be considered additional information that must be collected in the relevant eCRF. If the laboratory abnormality is a sign of a disease or syndrome, only the diagnosis needs to be recorded on the SAE Report Form or AE eCRF.

---

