2.4.5.1 Analysis of Adverse Events

The Treatment-Emergent Adverse Events (TEAE) is defined as any AE that:

- Occurs after first dosing of study medication and through the end of the study or up through 30 days after the last dose of study treatment, or
- Is considered treatment-related regardless of the start date of the event, or
- Is present before first dosing of study medication but worsens in intensity or the investigator subsequently considers treatment related.

Dose-limiting toxicity (DLT) is defined in protocol section 5.1.1 and collected in eCRF.

Adverse event incidence tables will be presented by cohort and total, the number (n) and percentage (%) of subjects experiencing an AE. In a subset of tables, also all occurrences will be counted providing a severity of occurrence of the AE. The denominator for computation of percentages is the Safety Population within each cohort.

Not treatment emergent AE(s) summary:

- Listing of (not treatment emergent) AEs showing cohort, subject identifier, SOC, PT, verbatim term, date and day of onset, end date/time, duration, outcome, severity, date of death (if relevant), relationship to study treatment, action taken, AE seriousness and criteria.

TEAE(s) summaries:

The following TEAE summaries will be generated for the Safety Population.

Overview of TEAEs, summarizing number (%) of subjects with any

- (related/all) TEAE
- (related/all) Serious TEAE
- DLT
- (related/all) TEAE leading to death
- (related/all) TEAE of grade 3 or higher
- (related/all) TEAE leading to drug interruption
- (related/all) TEAE of special interest (AESI)
- (related/all) TEAE leading to permanent discontinuation

- TEAEs by primary SOC and PT, showing number (%) of subjects with at least one TEAE, sorted alphabetically by SOC and decreasing incidence of PTs within SOC for the total column. This sorting order will be applied to all other tables, unless otherwise specified.
- TEAEs by PT, sorted by decreasing frequency in the total column.
- All at least possibly drug related TEAEs by primary SOC and PT, showing number (%) of subjects with at least one possibly related TEAE, sorted by sorting order defined above.
- All TEAEs by maximal severity, presented by primary SOC and PT, showing number (%) of subjects with at least one TEAE by severity (ie, mild, moderate, or severe), sorted by sorting order defined above.

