- Listing of TEAEs showing treatment group, subject identifier, SOC, PT, verbatim term, date and day of onset, end date/time, duration, outcome, severity, date of death (if relevant), relationship to study treatment, action taken, AE seriousness and criteria.

DLT summaries:

- DLTs by SOC and PT, showing number (%) of subjects with at least one DLT, sorted by sorting order defined above.
- Listing of DLTs showing cohort, subject identifier, SOC, PT, verbatim term, date and day of onset, end date/time, duration, outcome, severity, date of death (if relevant), relationship to study treatment, action taken, AE seriousness and criteria.

AESI summaries:

- Treatment-emergent AESI by category and PT, showing number (%) of subjects with at least one TEAE, sorted alphabetically by category and decreasing incidence of PTs within category for the total column. This sorting order will be applied to all other tables, unless otherwise specified.
- Listing of treatment-emergent AESI showing cohort, subject identifier, category, PT, verbatim term, date and day of onset, end date/time, duration, outcome, severity, date of death (if relevant), relationship to study treatment, action taken, AE seriousness and criteria.

Treatment-Emergent Suicidal Ideation and Behavior (SIB)

- Treatment-emergent SIB events will be summarized by treatment group, showing number (%) of subjects with at least one TEAE of suicidal ideation and behavior, and number (%) of subjects for each PT.
- A listing of suicidal ideations and behaviors will also be presented.
- Additional SIB analyses may be conducted as needed, such as follow-up time adjusted incidence rates of SIB event.

Serious TEAE(s) summaries:

- All serious TEAEs by primary SOC and PT, showing number (%) of subjects with at least one serious TEAE, sorted by sorting order defined above.
- All at least possibly related to ublituximab serious TEAEs by primary SOC and PT, showing number (%) of subjects with at least one possibly related serious TEAE, sorted by sorting order defined above.
- All serious TEAEs by seriousness criteria, presented by primary SOC and PT, showing number (%) of subjects with at least one serious TEAE by seriousness criteria.
- Listings of SAEs showing treatment group, subject identifier, SOC, PT, verbatim term, date and day of onset, end date/time, duration, outcome, severity, date of death (if relevant), relationship to study treatment, action taken, AE seriousness and criteria.

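### A laboratory value that makes the protocol withhold an infusion or withdraw a subject need not be recorded as an AE, so the withdrawal can be absent from the SAP's AE-based discontinuation tables

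*Protocol*

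**What the plan says.** **Laboratory values as AEs.** Protocol 10.7.2, repeated in 10.11.2, asks for an abnormal result to be entered as an AE "if they are associated with an overdose, require or prolong inpatient hospitalization, or are otherwise considered clinically significant by the investigator". Related symptoms, or a diagnosis that explains the value, are recorded as AEs in their own right.

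**Vital signs as AEs.** The same paragraph of 10.7.2 discourages reporting of vital-sign abnormalities, but makes an exception when "the vital signs abnormalities cause the patient to discontinue trial treatment".

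**Laboratory values that stop dosing.** Protocol 5.2 requires neutrophils and platelets within the normal range before each infusion and sets a limit of 5 times ULN for ALT and AST. A subject who fails is held for up to 48 hours. After that, "If all labs above do not return to within the acceptable range within 48 hours, the subject will not receive the ublituximab infusion", and the subject is withdrawn from the study. Protocol 6.2.1.1, a set of recommendations for toxicity attributed to ublituximab, asks for no action on neutropenia, thrombocytopenia or anemia up to Grade 2 (growth factor may be considered for Grade 2 neutropenia) and advises a hold at Grade 3 or 4.

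**What the SAP counts.** SAP 2.4.5.1 draws its tolerability tables from AE records. One line of the overview reads "related/all) TEAE leading to permanent discontinuation"; another covers drug interruption; a later table breaks discontinuations down by SOC and PT. DLTs are tabulated in the same way: "DLTs by SOC and PT, showing number (%) of subjects with at least one DLT".

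**The concern.** The protocol's rule for withholding treatment in 5.2 rests on laboratory values, yet the rule that turns laboratory values into AEs does not mention a withheld infusion or a withdrawal. Whether an AE record exists then depends on the investigator's view of clinical significance, which can differ between sites.

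Tolerability is one of the stated purposes of the design (Synopsis; SAP 1.1), and Protocol 5.1.3 has the DSMB review adverse events at the end of each cohort. If a laboratory-driven withdrawal has no AE, the cohort looks better tolerated in the AE tables than it was. With 6 subjects randomized to ublituximab per cohort, one subject is enough to change the picture.

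**Working it through.** The documents state no figure on this point, so there is nothing to reproduce. The check is a comparison of texts, followed by an illustration of scale.

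**Step 1. Triggers side by side.**

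| Event | Vital signs (10.7.2) | Laboratory values (10.7.2, 10.11.2) |
|---|---|---|
| Seriousness or hospitalization | listed (any SAE criterion) | listed (hospitalization) |
| Overdose | not listed | listed |
| Discontinuation of treatment | listed | not listed |
| Infusion held or not given | not listed | not listed |
| Investigator's judgement | listed | listed |

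**Step 2. Can a value stop dosing without being judged clinically significant?** Take a neutrophil or platelet count slightly below the laboratory's lower limit that has not recovered after 48 hours. Under 5.2 the subject is not infused and leaves the study. Under 6.2.1.1 a cytopenia up to Grade 2 calls for no dosing action. An investigator who follows 6.2.1.1 in judging significance has a reasonable ground for not recording an AE, while 5.2 still removes the subject. The two sections contradict each other and must be reconciled; this review takes no view on which is right.

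**Step 3. Where would the subject appear?**
- *AE tables (SAP 2.4.5.1):* not in the discontinuation lines or tables, because there is no TEAE to count.
- *Laboratory tables (SAP 2.4.5.2):* as a high or low value and in an H/L shift table. Protocol 10.7.2 promises incidence by maximum CTCAE grade; SAP 2.4.5.2 does not include it. Neither links a value to a treatment action.
- *Disposition (SAP 2.3):* the line on stopped treatment is worded for subjects who stop but remain under assessment. Those withdrawn under 5.2 are asked to enter follow-up, so some may fit. Protocol 9.4 does promise reasons for study discontinuation, but such a reason is not a coded, graded, causality-assessed event.
- *Exposure (SAP 2.1.2):* as fewer infusions received. A hold that resolves within 48 hours matches none of the listed variables.

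**Step 4. Scale for one hypothetical subject.** Inputs: 6 subjects randomized to ublituximab per cohort (Protocol 5.1); 6 + 2 = 8 once the placebo subjects switch, which is the SAP denominator because its Safety Population takes everyone dosed with ublituximab; 6 cohorts × 8 = 48 if all six are filled. Intervals are exact (Clopper-Pearson), two-sided 95%. For 0 of n, the upper limit is 1 − 0.025^(1/n); for n = 6 that is 1 − 0.541 = 0.459.

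| Denominator | Event recorded | Event not recorded |
|---|---|---|
| 6 | 1/6 = 16.7% (0.4 to 64.1) | 0% (0 to 45.9) |
| 8 | 1/8 = 12.5% (0.3 to 52.7) | 0% (0 to 36.9) |
| 48 | 1/48 = 2.1% (0.1 to 11.1) | 0% (0 to 7.4) |

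**The case against.** **The laboratory rule is not restrictive.** A reader might infer that laboratory values become AEs in the listed cases alone. The text does not say so. It is an inclusion list that ends in an open clause, "or are otherwise considered clinically significant by the investigator"; the discouraging language applies to vital signs. Vital signs need an explicit discontinuation trigger because their default is non-reporting, so the contrast in Step 1 is weaker evidence than it first appears. Protocol 10.6 also counts an abnormal laboratory finding among possible AEs, and symptoms and diagnoses have their own route. This objection stands: omission is permitted, not required. But two sections that sites can read differently do not give uniform recording.

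**DLTs have their own route.** A reader might also infer that the rule removes laboratory DLTs from the DLT tables. It does not. Under 5.1.1 a qualifying event is a DLT by default, unless it is clearly unrelated or is set aside after a documented meeting, and SAP 2.4.5.1 says that DLTs are collected in the eCRF. What remains is smaller: the DLT table and listing use SOC, PT, verbatim term and AE seriousness, and neither document says outright that a laboratory DLT must have an AE record.

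**Drug interruption is undefined.** The SAP never says whether a pre-infusion hold counts as drug interruption, so it cannot be claimed that such holds are missing from that line. This stands, and it is itself a point to clarify.

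**The number affected could be zero.** It is tempting to apply the more-than-20% class for neutropenia and thrombocytopenia in Protocol 8.1.1.1 to 48 subjects. That class describes events already recorded as related AEs, is not specific to MS, and says nothing about holds or withdrawals. It cannot estimate unrecorded events.

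**The data are not lost.** Laboratory values, infusions received and reasons for discontinuation are collected. That is true, but Step 3 shows that each backstop is partial. CRF completion guidelines, which might settle the matter, are not among the documents.

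**Conclusion.** The point holds in a limited form. As written, the plan allows a withdrawal forced by the laboratory rule in 5.2 to have no AE record, and so to be absent from the SAP's AE-based discontinuation tables. It does not prescribe that outcome, and it does not by itself take laboratory DLTs out of the DLT tables.

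The size is one subject at a time: 16.7% or 12.5% against 0% in a cohort. The exact intervals overlap heavily, so this is about how a small cohort's table reads rather than about any formal inference. The frequency is unknown.

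The conclusion assumes that sites apply 5.2 as written, that some investigators would not call a mildly low count clinically significant, and that no unseen CRF guideline already requires an AE. It is a reporting gap that is cheap to close and worth closing; it does not threaten the primary B-cell endpoint.

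**What to change.** 1. **Protocol 10.7.2 and 10.11.2:** state that a laboratory abnormality is recorded as an AE, with the action-taken field completed, when it leads to an infusion being held or not given, or to withdrawal from treatment or study.
2. **Same sections:** cross-reference 5.1.1 so that every laboratory DLT has a coded AE record, and align the wording with the AE definition in 10.6.
3. **Protocol 5.2 and 6.2.1.1:** the sponsor should reconcile these passages. The recording change does not depend on how that is resolved.
4. **SAP 2.4.5.1:** say whether a pre-infusion hold counts as drug interruption.
5. **SAP 2.4.5.2:** restore the table of laboratory toxicity by maximum CTCAE grade that Protocol 10.7.2 promises.

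If data collection has ended, a SAP listing that links pre-dose laboratory values to held or omitted infusions and withdrawals would recover most of the information.

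The cost is a short clause in two protocol sections, a matching line in the CRF guideline, one SAP table, one SAP definition and a few more AE records. Reported discontinuation rates may become slightly less favourable. None of the recording or SAP changes alters a dose, hold or withdrawal rule.
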